11.1.4.4.1. Laboratory assays

HIV EIA and HIV Western blot or immunochromatographic test: Either Thai or U.S. FDA-approved kits maybe used.

HIV nucleic acid tests: plasma collected in a suitable anti-coagulant (EDTA or ACD) will be assayed for HIV NAAT using at least one nucleic acid test platform. Supplemental nucleic acid tests may also be incorporated.

Samples that are Western Blot or immunochromatographic test indeterminate may also be subject to supplemental Nucleic Acid testing at the discretion of the PI or designee.

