5.9. Study Population

A total of 80 healthy, HIV-uninfected participants at a low risk for HIV infection, available for 12 months, who were randomized to receive active vaccine in RV306 and completed all vaccinations will be enrolled. A total of 274/300 (91.3%) active recipients from Groups 2, 3, 4a, and 4b received all vaccinations and completed all study visits in RV306.

Each site will recruit participants who participated in RV306 at their respective sites, however recruitment may also include participants who participated in RV306 at the site in Chiang Mai University if the participant is willing to be enrolled and followed at one of the two Bangkok sites. It is anticipated that up to 110 prior RV306 participants will be screened in order to enroll 80 participants into RV546. As much as possible, an equivalent proportion of male and female participants will be enrolled into each arm of the study.

Study staff and participants will be blinded to vaccine/placebo and full dose/fractional dose assignment. As a byproduct of the sequential enrollment of the vaccine/placebo groups, study staff will not be blinded to a participant's receipt of ALFQ. Groups 1 and 2 (without ALFQ adjuvant) will be enrolled first in a randomized, double-blinded manner. Enrollment into Groups 1 and 2 will begin with no more than two participants per site per week for the first two weeks. Once at least 7-days of safety data is available from the first eight participants enrolled across Groups 1 and 2, the Safety Monitoring Committee (SMC) will review 7-days of safety data from these participants to determine whether enrollment can continue. Enrollment into Groups 1 and 2 will be unrestricted after any safety concerns raised by the SMC are addressed and the Sponsor has given their approval for continuation of enrollment. Enrollment into Groups 3 and 4 will commence after enrollment into Group 1 and Group 2 has been completed, the SMC has reviewed 7-days of safety data from all Group 1 and 2 participants, and the Sponsor gives their approval. Enrollment into Groups 3 and 4 will follow a similar approach with no more than two participants per site per week for the first two weeks, followed by an SMC review of 7-days of safety data from the first eight participants enrolled across both Groups, and Sponsor approval before enrollment can continue unrestricted in Groups 3 and 4. The PI, investigators and study participants will remain blinded to vaccine and placebo allocation.

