7.3.2. Blinding

The PI, study staff, and participants will be blinded as to receipt of active vaccines or placebo but the PI and study staff will not be blinded to group allocation as it pertains to the inclusion of ALFQ. Since the vaccines and placebos are not identical in appearance, to preserve blinding the material inside the syringe will be masked by the pharmacist. In addition, the pharmacy staff preparing the vaccine syringes will not be involved in the clinical assessment of participants and will be instructed not to comment on the appearance of experimental agent to study staff. For all participants, the volume of injections will be consistent.

Pharmacy staff will be trained in GCP and instructed not to discuss the vaccine randomization lists, codes, or participant assignments with study personnel. Pharmacy staff will be required to sign a confidentiality agreement and will be the only person(s) on site who will know the randomization assignment. The randomization assignment will not appear on any label or source document leaving the pharmacy. Samples will be labeled on site using labels containing participant study numbers, protocol number and visit number. The samples will be accompanied by a specimen tracking form that records the study number, date and time of sample collection.

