Since HIV-1 binding antibody and Western Blot/immunochromatography results (Section 5.6.1.6) may reflect vaccine or placebo assignments, access to such data will be limited to the laboratory personnel who are performing the tests and managing the data, and the independent statistician. If diagnostic testing of original and verification samples reveals true HIV infection, the participant will be notified by the clinic staff / physician. The PI and Sponsor will be informed of HIV infection by the laboratory. HIV-infected participants will be informed about their HIV infection, but the participant, study site investigators, Sponsor, and manufacturer staff will remain blinded as to their treatment assignment until the study is closed and the database is locked. Diagnostic HIV testing will utilize a sequence of validated tests that will differentiate between vaccine-induced seroreactivity and true HIV infection. Information to the study staff of each vaccine trial site will not include the results of specific tests but will state only HIV "infected" or "not infected", or that repeat testing is needed (as in the case of need for a verification specimen). Report of results will be standardized so that the timing of HIV test reporting does not compromise the double-blind nature of the trial, as a result returned immediately after EIA testing could signal the clinical team that this specimen did not require the additional testing which would be needed if vaccine had induced an antibody response. Some participants may be tempted to know their assignment to vaccine or placebo through voluntary

HIV testing. Participants will be actively discouraged from having HIV testing outside of the trial protocol. If specific needs arise, the research team will provide HIV testing and assist participants who need HIV status determination. Further, participants will be counseled that if they have engaged in behavior that may have increased risk of exposure to HIV, they should have HIV testing done and this should be done through the vaccine trial system.

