11.1.4.4. HIV Diagnostic Algorithm

Diagnostic HIV testing will utilize a sequence of validated tests that will differentiate between vaccine induced seroreactivity and true HIV infection. Information to the study staff of each vaccine trial site will not include the results of specific tests but will state only HIV "infected" or "not infected", or that repeat testing is needed (as in the case of need for a verification specimen). Report of results will be delayed to at least 10 days from blood collection so that the timing of HIV test reporting does not compromise the double-blind nature of the trial, as a result returned immediately after EIA testing could signal the clinical team that this specimen did not require the Western blot or immunochromatographic testing which would be needed if vaccine had induced an antibody response.

An HIV-1 EIA assay will be utilized throughout the course of the study. If the EIA is reactive, the test will be repeated in duplicate. If repeatedly reactive, an HIV Western blot or immunochromatographic test will be performed. If the Western blot or immunochromatographic test is positive, HIV nucleic acid testing (NAAT) will be performed on the plasma specimen stored at -70°C or lower. If the NAAT is positive, a diagnosis of HIV infection is suspected. Notification from the lab that a verification specimen is required is sent to the CRC at the research site and the participant is called back for counseling and repeat blood draw. A second blood specimen (verification specimen) will be obtained for complete repeat HIV diagnostics. If the second plasma specimen is positive both serologically and by NAAT, a diagnosis of HIV infection is considered established. If the verification specimen is not positive (negative or indeterminate), the participant will be counseled that one additional blood collection (second verification specimen) for retesting will be necessary. If results of this repeat verification specimen are positive, infection is established; if not positive, the participant will be informed that he/she is not HIV infected and will return to the protocol's regular visit schedule. This process is outlined below in the HIV Testing Algorithm in [Figure 2](#).

Figure 2: HIV Testing Algorithm

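### Giving the blinded PI or an unspecified designee discretion over nucleic acid testing of indeterminate samples conflicts with the restriction on those same results in Section 7.3.2

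*Protocol*

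**What the plan says.** Four statements in the protocol bear on this.

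- **Who is blinded.** Section 7.3.2: "The PI, study staff, and participants will be blinded as to receipt of active vaccines or placebo". Section 5.9 repeats it: "The PI, investigators and study participants will remain blinded to vaccine and placebo allocation". SAP Section 4.5.5 takes the same position.
- **Who may see the confirmatory serology.** Section 7.3.2 gives the reason, that "Western Blot/immunochromatography results (Section 5.6.1.6) may reflect vaccine or placebo assignments", and the rule: "access to such data will be limited to the laboratory personnel who are performing the tests and managing the data, and the independent statistician". The PI is not on that list. What the PI does learn is stated separately: "The PI and Sponsor will be informed of HIV infection by the laboratory".
- **What the site is told.** Section 11.1.4.4: "Information to the study staff of each vaccine trial site will not include the results of specific tests but will state only HIV", followed by three permitted messages: infected, not infected, or a repeat is required. The same section holds back reporting for at least 10 days after the blood draw, so that turnaround time does not show whether a confirmatory test was run.
- **Who decides about indeterminate samples.** Section 11.1.4.4.1 reads: "Western Blot or immunochromatographic test indeterminate may also be subject to supplemental Nucleic Acid testing at the discretion of the PI or designee".

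**The concern.** A decision about a particular indeterminate sample has to be made by someone who knows that the sample is indeterminate. Asking the PI therefore tells the PI that this participant was repeatedly reactive on EIA and had an indeterminate confirmatory test. That is more than the reporting delay is meant to hide, since the delay conceals even whether the confirmatory test took place.

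The PI belongs to the group whose judgement the blind protects. Investigators assign relatedness and severity (Protocol 11.3, 11.3.1, 11.7.1). Adverse events with their attribution are among the primary safety endpoints (SAP 3.2.1). Site PIs or their designees sit on the PSRT (Protocol 11.5), and three of the four pause criteria in Section 7.6.1 depend on judged relatedness. Section 7.3.3 provides a controlled route for unblinding and requires accidental unblinding to be reported; a referral under Section 11.1.4.4.1 passes through neither.

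**Working it through.** The protocol states no figure to reproduce. The check is to set the sections side by side and then ask what a disclosed result could influence.

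**1. Is there a written exception?** Section 7.3.2 names the permitted readers and leaves out the PI. Section 11.1.4.4 leaves out site staff. Section 11.1.4.4.1 names the PI or a designee, without requiring that the designee come from the permitted group. None of these sections, nor SAP 4.5.5, gives an exception or describes a masked request. The conflict is unresolved in the text.

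**2. Is the clause redundant?** In the text of Section 11.1.4.4 the automatic trigger is a positive result: "If the Western blot or immunochromatographic test is positive, HIV nucleic acid testing (NAAT) will be performed on the plasma specimen". No step is written there for an indeterminate first result, so Section 11.1.4.4.1 is the only route to nucleic acid testing in the text for such a sample. Figure 2 was not legible in the copy reviewed and should be checked.

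**3. When could a result arrive?** After vaccination, HIV tests are scheduled at Days 14, 168 and 336 (Table 3). The Day 14 window opens at 14 − 2 = Day 12. Solicited reactions are recorded for 7 days, and the Day 7 visit window closes at 7 + 2 = Day 9. On schedule, the solicited data are complete before the first post-dose HIV sample is drawn. What remains open is later unsolicited events, their attribution, and pause judgements that rest on them.

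**4. How informative is an indeterminate result?** The planned totals are 64 vaccine and 16 placebo, so the odds of vaccine before any test are 64:16 = 4:1, or 64/80 = 80%. Let p_v and p_p be the chances of an indeterminate result in vaccine and placebo recipients. Then

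odds of vaccine after an indeterminate result = 4 × (p_v / p_p).

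If p_v = p_p the probability stays at 80%. As p_p falls towards zero it approaches 100%. The documents give neither rate. Every participant had active vaccine with a late boost in RV306 (Protocol 8.4), so p_p need not be near zero. Vaccine recipients might also become positive rather than indeterminate, so strictly even the direction of the cue is unknown.

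**5. Which analyses could be touched?** The formal adverse event tests in SAP 7.1.1 compare ALFQ with no ALFQ and full with fractional dose, all among active recipients. Staff already know ALFQ status, and nothing in the documents suggests that the serology reveals dose. Placebo enters only as a fifth descriptive group, compared by overlap of confidence intervals. The exposure is in attribution tables and pause decisions, not in the two planned tests.

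**The case against.** The strongest defence is that the clause is permissive and says PI or designee. A designee could be the laboratory investigator, who according to Appendix A supervises laboratory work and has no contact with participants, or the PI could give the laboratory one standing instruction. Either would avoid disclosure. This stands in part: a reader might infer that the discretion cannot be used without the PI seeing individual results, and the wording does not go that far. But the text neither limits the designee nor provides for a standing instruction, and it names the PI first.

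The second defence is prior RV306 vaccination, which makes residual seroreactivity possible in placebo recipients. A reader might reason that an indeterminate Day 14 result after a non-reactive screening test points to vaccine. The documents do not give the PI the screening results. Not being consulted at screening would suggest at most that the earlier sample was not indeterminate; it would not separate non-reactive from positive. This defence weakens the cue. It does not remove the conflict, because Section 7.3.2 restricts these results in this same previously vaccinated population.

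Third, the Independent Safety Monitor separately assesses relatedness for every serious event (Protocol 11.4). That limits the harm for serious events but not for non-serious ones.

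**Conclusion.** The contradiction between Sections 7.3.2 and 11.1.4.4 on one side and Section 11.1.4.4.1 on the other is real and should be reconciled. Its reach is modest: possible partial unblinding of the PI or site designee, for participants with an indeterminate post-dose result, in judgements made from Day 14 onward. This assumes that the discretion is exercised sample by sample by someone outside the permitted group.

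Two stronger conclusions are not supported. A reader might infer that the primary safety endpoint as a whole is unblinded. The solicited component closes before the first post-dose HIV test, and the formal comparisons are among active groups only. A reader might also attach a count, for instance by applying an assumed 10% to 50% indeterminate rate to the 64 vaccine recipients (0.10 × 64 = 6.4; 0.50 × 64 = 32). No such rate appears in the documents, and the count would further require that every sample is referred to the PI and that each one reveals assignment. The number affected cannot be estimated.

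**What to change.** Reconcile Protocol Sections 7.3.2, 11.1.4.4 and 11.1.4.4.1 so that they state three things:

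1. The decision on supplemental testing of indeterminate samples is taken by personnel who already have access to those results under Section 7.3.2. They hold test results and need not know assignments, so no new unblinded role is created.
2. They act under a laboratory procedure written in advance. The sponsor sets its content; this point concerns only who decides and who sees the result, not what the diagnostic rule should be.
3. The site receives only the status wording already permitted in Section 11.1.4.4.

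Figure 2 should be checked for agreement. The cost is about one sentence in the protocol and one line in the laboratory SOP. No visit, sample or analysis changes.

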11.1.4.5. Pregnancy Screen

Pregnancy tests will be performed on all female participants at screening; prior to the vaccination; at Visits 4, 5, and 6; and prior to optional procedures (mucosal secretion collection, leukapheresis, sigmoid biopsy, and inguinal lymph node biopsy) as indicated in the SOE. No vaccine or optional procedures will be performed if the pregnancy test is positive.

11.2. Adverse Event Reporting

The following terms, as defined by 21 CFR 312.32, apply to IND safety reporting.

11.2.1. Adverse Event and Suspected Adverse Reaction

An AE is any untoward medical occurrence in a clinical investigation participant administered a pharmaceutical product and does not necessarily have a causal relationship with this product. An AE can therefore be any unfavorable and unintended sign (including an abnormal laboratory finding), symptom, or disease temporally associated with the use of an investigational product, whether or not related to the investigational product. (International Conference on Harmonization (ICH) E6)

An AE is considered to be any adverse change or exacerbation from a baseline condition that occurs following the administration of an investigational product whether or not the event is considered related to the investigational product. Examples of this include but are not limited to the following:

- Adverse changes including new signs and symptoms, intercurrent illness modifying the clinical course, or the worsening of a baseline condition including the increased frequency of an event or an increased intensity of a condition.
- Concomitant disease with onset or increased severity after the start of investigational product administration.
- A new pattern in a pre-existing condition, occurring after the receipt of investigational product that may signal a clinically meaningful change.
- Clinically significant changes in laboratory values.

A suspected adverse reaction is any AE for which there is a reasonable possibility that the investigational product caused the AE, with “reasonable possibility” meaning there is evidence to suggest a causal relationship between the investigational product and the AE. This implies a

lesser degree of certainty about causality than adverse reaction, which means any AE caused by an investigational product.

11.2.2. Solicited Adverse Event

A solicited AE is a predetermined event, identified in the Investigator's Brochure, which may reflect safety concerns related to the investigational product. AEs that will be solicited and assessed for this study include localized post-vaccination reactions such as erythema, induration, pain and tenderness, swelling and limitation of leg movement, and systemic reactions such as fever, tiredness, chills, myalgia, arthralgia, headache, nausea, and rash. These reactogenicity events will be recorded 30 minutes post-vaccination and during the 7 days following the vaccination. Any local or systemic reactogenicity events beyond 7 days will be reported as an AE.

11.2.3. Serious Adverse Event or Serious Suspected Adverse Reaction

As defined in 21 CFR 312.32, an AE or suspected adverse reaction is considered "serious" if, in the view of either the investigator or sponsor, it results in any of the following outcomes:

- Death
- Life-threatening AE
- Inpatient hospitalization or prolongation of existing hospitalization
- Persistent or significant incapacity or substantial disruption of the ability to conduct normal life functions
- Congenital anomaly/birth defect.

An AE or suspected adverse reaction is considered "life-threatening" if, in the view of either the investigator or sponsor, its occurrence places the participant at immediate risk of death. It does not include an AE or suspected adverse reaction that, had it occurred in a more severe form, might have caused death.

Important medical events that may not result in death, be life-threatening, or require hospitalization may be considered serious when, based upon appropriate medical judgment, they may jeopardize the participant and may require medical or surgical intervention to prevent one of the outcomes listed in this definition. Examples of such medical events include allergic bronchospasm requiring intensive treatment in an emergency room or at home, blood dyscrasias or convulsions that do not result in inpatient hospitalization, or the development of drug dependency or drug abuse.

11.2.4. Unexpected Adverse Event or Unexpected Suspected Adverse Reaction

An AE or suspected adverse reaction is considered "unexpected" if it is not listed in the investigator brochure or is not listed at the specificity or severity that has been observed. An unexpected AE for this study refers to an adverse vaccine experience that has not been previously observed (not included in the investigator brochure) rather than from the perspective of such experience not being anticipated from the pharmacological properties of the vaccine. Expected Events are described in the Investigator Brochure and the Clinical MOP. All other events would be considered as unexpected.

11.2.5. Other Adverse Events

All other AEs (those that do not fall under the categories of solicited, an SAE or unexpected) that are identified by site staff, study physicians or the PI, will be documented in the participant's clinic records and entered in the study CRFs, including AESIs as listed in [Appendix H](#).

11.3. Relationship to Investigational Product

The investigator must assign a relationship of each AE to the receipt of the investigational product. The investigator will use clinical judgment in conjunction with the assessment of a plausible biologic mechanism, a temporal relationship between the onset of the event in relation to receipt of the investigational product, and identification of possible alternate etiologies including underlying disease, concurrent illness or concomitant medications. The relationship of the vaccination to an AE will be determined based on the following definitions:

Not related: No relationship to investigational product. Applies to those events for which evidence exists that there is an alternate etiology.

Unlikely: Likely unrelated to the investigational product. Likely to be related to factors other than investigational product but cannot be ruled out with certainty.

Possible: An association between the event and the administration of investigational product cannot be ruled out. There is a reasonable temporal association, but there may also be an alternative etiology such as the participant's clinical status or underlying factors including other therapy.

Probable: There is a high degree of certainty that a relationship to the investigational product exists. There is a reasonable temporal association, and the event cannot be explained by known characteristics of the participant's clinical state or factors including other therapy.

Definite: An association exists between the receipt of investigational product and the event. An association to other factors has been ruled out.

